3.4.4 Additional Analysis

3.4.4.1 Analysis of mRS (0-6 scale)

An analysis will be performed using the nonparametric Wilcoxon test and the Mann-Whitney U test to determine if 90 day mRS (0-6 scale) differs between high-dose RNS60 (1.0 mL/kg/h RNS60) vs. placebo, low-dose (0.5 mL/kg/h RNS60) vs. placebo, and between combined dose vs. placebo.

The analysis will be carried out using the NPAR1WAY procedure in SAS where the model will include the mRS score at Day 90 as the analysis response variable, treatment as the CLASS variables, and will include the frequency of subjects within each mRS score category. The following SAS code and procedures will be performed using three sets of data: Placebo and low dose; Placebo and high dose; and Placebo and the two active doses considered as a single group. The sample SAS code is provided below:

A large block of text has been redacted with black ink, appearing as a series of horizontal and vertical lines of varying lengths.

The sum of scores and expected score under null hypothesis across each group will be displayed along with the one-sided p-value for each treatment vs. placebo. Additionally, an estimate of the probability that a random member of each treatment arm performs better than a random member of each placebo arm will be provided using the following steps:

1. Using the Wilcoxon scores, the following U-Statistic will be calculated for each arm:
$$U1 = R1 - \left[\frac{n1(n1+1)}{2} \right]$$
; where R is the sum of Ranks (sum of scores) for the treatment arm, and n1 is the number of subjects in the that arm.

2. The concordance probability will be calculated as follows:

$$f = \frac{U_1}{n_1 n_2}; \text{ where } U_1 \text{ is the U-Statistic calculated above and } n_1 \text{ and } n_2 \text{ are the number of subjects in each arm.}$$

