3.2.2 Secondary Efficacy Outcomes

Secondary outcomes include:

- 1) The mean mRS score at Day 90, where a lower score is better.
- 2) A reduction in mortality rate, as defined by a lower event rate on a Kaplan Meier survival curve
- 3) The mean NIHSS score post randomization, where a lower score is better
- 4) The proportion of patients with worsening of stroke over the 90-day study period
- 5) The mean BI at Day 90

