2.3.2 Secondary Efficacy Endpoints

Secondary endpoints include:

- 1) Disability based on the mRS score at Day 90 as a binary outcome (0-2, 3-6).

The mRS is a commonly used valid and reliable clinician-reported outcome measure in subjects who have suffered a stroke. It measures functional recovery (the degree of disability or dependence in daily activities in a 6-point disability scale with possible scores ranging from 0 to 5. A score of 6 is used for subjects who expire.

Table 2. Description of scores in mRS

| Score | Description |
|-------|---|
| 0 | No symptoms at all |
| 1 | No significant disability despite symptoms; able to carry out all usual duties and activities |
| 2 | Slight disability: unable to carry out all previous activities but able to look after own affairs without assistance |
| 3 | Moderate disability: requiring some help, but able to walk without assistance |
| 4 | Moderately severe disability: unable to walk without assistance and unable to attend to own bodily needs without assistance |
| 5 | Severe disability; bedridden, incontinent, requiring constant nursing care and attention |
| 6 | Death (at hospital or after discharge) |

The post-dose mRS score will be obtained at Day 6 (or discharge), and Days 30 and 90. Premorbid mRS status may be obtained at any time, but ideally at the Day 1 or 2 visit. The mRS will only be scored by those trained and certified in the use of this scale.

- 2) Infarct volume of stroke at 48h.

Infarct progression/regression as measured by MRI of the brain in RNS60 versus placebo control participants will be calculated from the 48h imaging and compared to the

immediate post-thrombectomy MRI. The volume of injured tissue on Fluid Attenuated Inversion Recovery (FLAIR) and T2 weighted images will be compared.

3) NIHSS score at hour 24.

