3.1.7 Handling of Death

Subjects who die during the study will be scored as follows for all scheduled visits following the death: 6 for mRS, 42 for NIHSS and 0 for BI. The value 6 for mRS is part of the mRS definition. The values for NIHSS and BI are conventions, consistent with the worst possible score.

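### The concordance probability in SAP 3.4.4.1, as printed, measures how often treated patients do worse on the mRS, although it is labelled as how often they do better

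*SAP*

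**What the plan says.** SAP 3.4.4.1 sets out a rank analysis of the full Day 90 mRS for three contrasts: high dose, low dose and combined doses, each against placebo.

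- Variable ranked: "the model will include the mRS score at Day 90 as the analysis response variable". No readable text reverses the score or the rank order.
- Displayed output: "The sum of scores and expected score under null hypothesis across each group will be displayed", with a one-sided p-value.
- Added effect estimate: "an estimate of the probability that a random member of each treatment arm performs better than a random member of each placebo arm".
- Step 1: "Using the Wilcoxon scores, the following U-Statistic will be calculated for each arm". The formula is U1 = R1 - n1(n1+1)/2, "where R is the sum of Ranks (sum of scores) for the treatment arm".
- Step 2: f = U1/(n1 n2), with U1 described only as the statistic from step 1.

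On the direction of the scale, Protocol 3.2.2 has "The mean mRS score at Day 90, where a lower score is better", SAP 2.3.2 has "A score of 6 is used for subjects who expire", and SAP 3.1.7 scores patients who die at "6 for mRS, 42 for NIHSS and 0 for BI".

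**The concern.** The label and the formula point in opposite directions. The rank sum of an arm grows as its values grow, and on the mRS larger values are worse outcomes. A U built from the treatment arm's rank sum therefore counts pairs that the treated patient loses, while the label says it counts pairs that the treated patient wins.

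A reader who trusts the label would read a benefit of RNS60 as harm, or harm as benefit. The same formula serves all three contrasts. This is an additional analysis, but it is the only formal between-arm comparison of the whole 0-6 scale in the SAP: the hierarchical mRS endpoint is split into 0-2 against 3-6, and the bar graphs in SAP 3.4.2 are descriptive. Protocol 9.3.3 says the efficacy results are meant to supply effect sizes for a later trial, and f is the effect size of this analysis. The SAP also takes precedence over the protocol (SAP 1 and 6.4), so no other text overrides the formula.

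**Working it through.** The plan gives a formula and a label but no number, so there is no figure to reproduce. The check asks what the printed formula estimates.

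**Inputs.** Formula, ranked variable and arm are from SAP 3.4.4.1. Scale direction is from Protocol 3.2.2 and SAP 2.3.2. About 33 patients per arm follows from 100 patients allocated 1:1:1 (SAP 2.2.1 and 2.2.4). Two things are assumed: ordinary Wilcoxon scores (ascending ranks, mid-ranks for ties) and the mRS counts used for illustration.

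**Identity.** With mid-ranks, the treatment arm's U1 is the number of treated-placebo pairs in which the treated patient has the higher mRS, plus half the tied pairs. Hence

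f = U1/(n1 n2) = P(treated worse) + 0.5 P(tie).

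Computing f by the formula and by direct pair counting on 2000 random 0-6 data sets gave the same value each time (largest difference about 1e-16).

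**Limiting case.** All 33 treated patients score 0 and all 33 placebo patients score 6. Then R1 = 33 × 34/2 = 561, U1 = 561 - 561 = 0 and f = 0, although every treated patient did better. Swapping the arms gives f = 1.

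**High dose v placebo, 33 v 33 (assumed data).** Counts at mRS 0 to 6: treated 5, 7, 7, 4, 4, 3, 3 (mean 2.48); placebo 3, 5, 7, 5, 5, 3, 5 (mean 3.00).

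- R1 = 1018.5, against 33 × 67/2 = 1105.5 expected under the null.
- U1 = 1018.5 - 33 × 34/2 = 457.5. Placebo: R2 = 1192.5, U2 = 1192.5 - 561 = 631.5. Check: 457.5 + 631.5 = 1089 = 33 × 33.
- Printed f = 457.5/1089 = 0.420. Placebo-arm version = 631.5/1089 = 0.580.
- Direct pair counts: treated better 550, tied 163, worse 376. (376 + 81.5)/1089 = 0.420; (550 + 81.5)/1089 = 0.580.

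**Combined doses v placebo, 66 v 33.** This adds an assumed low-dose arm with counts 4, 6, 7, 5, 4, 3, 4 (mean 2.73).

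- R1 = 3167 (expected 3300); U1 = 3167 - 66 × 67/2 = 956; U2 = 2178 - 956 = 1222.
- Printed f = 956/2178 = 0.439; correct direction 1222/2178 = 0.561.
- Pair counts: better 1058, tied 328, worse 792.

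**Low dose v placebo, 33 v 33.** Subtracting the high-dose pairs from the combined pairs leaves better 508, tied 165, worse 416. Printed f = (416 + 82.5)/1089 = 0.458; correct direction (508 + 82.5)/1089 = 0.542.

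**Ties.** The strict probability of doing better is 550/1089 = 0.505 for the high dose and 1058/2178 = 0.486 for the combined doses. Even with the direction put right, f is P(better) plus half the ties, and not P(better) alone. Ties are about 15% of pairs here (163/1089 and 328/2178).

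**What does not change.** In the high-dose example z = -1.13 and the one-sided p is 0.13, whichever way f is written. Noether's sample size, (1.960 + 0.842)² / (12 × 0.25 × (f - 0.5)²), is about 410 in total from either 0.420 or 0.580, because it depends only on the distance from 0.5.

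**The case against.** The strongest objection is that the text leaves the arm unspecified and does not actually name the wrong one. Step 1 computes U for every arm, and step 2 does not say which U enters f. Elsewhere the SAP uses the term treatment arm for any randomised arm, placebo included (for example SAP 3.4.2 and Appendix D). On that reading both U values exist, and the placebo one gives the intended direction. The SAS code is also blacked out and could reverse the score or use the placebo U.

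Part of this stands. The readable text does not prove that a wrong number will be reported. But the sentence introducing the steps sets the treatment arm against the placebo arm, and step 1 then defines R for the treatment arm, so the active-arm reading is the natural one. On the other reading, the text allows two answers (0.420 or 0.580 in the example), of which only one has the labelled direction. Either way the printed rule needs correcting.

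It is also fair that this is a descriptive figure outside the hierarchy, and that the displayed rank sums and the mRS bar graphs would let an attentive reader notice the reversal. That limits the harm but does not make the label right. The point about ties also stands: reversing the direction alone does not make f equal to its label, so the tie convention has to be part of the correction.

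**Conclusion.** The concern holds. As printed, f equals P(treated worse) + 0.5 P(tie) under a label that says the treated patient does better. In the illustrations a benefit is shown as 0.420, 0.458 and 0.439 (high, low and combined dose) where the correctly directed values are 0.580, 0.542 and 0.561. The identity itself does not depend on these assumed counts; it rests on ascending mid-ranks of the unreversed mRS and on U1 coming from the active arm, as step 1 says. The consequence is one descriptive estimate per contrast reported in the wrong direction. The Wilcoxon test, its p-value, the 15-step hierarchy and any sample size based on the distance of f from 0.5 are unaffected. It should be corrected before results are reported.

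**What to change.** In SAP 3.4.4.1, step 2, define f = 1 - U1/(n1 n2) with U1 taken from the active arm. Using the placebo arm's U divided by n1 n2, or ranking 6 - mRS, is equivalent. State which arm's U is used, that f is the probability of a better score plus half the probability of a tie, and that f above 0.5 favours RNS60. The readable text does not give the direction of the one-sided p-value, so it should be stated in the same place.

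The sponsor should check whether the blacked-out code already reverses the score or uses the placebo-arm U. If it does, only the printed text changes. If it follows the printed formula, one line of code changes as well. Data, test and hierarchy stay as they are.

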3.4.4.2 Correlation Analysis between Infarct Volume and Clinical Outcomes

Correlation between infarct volume at different timepoints and clinical outcomes (mRS, NIHSS, BI) at 90 days will be measured using Spearman's correlation. Correlation will be performed for the high-dose RNS60, low-dose, and combined dose. Spearman's correlation coefficient and the corresponding p-value will be presented for each treatment.

The following outcomes will be evaluated:

- Correlation between infarct volume at 48 hours and mRS at 90 days
- Correlation between infarct volume at 48 hours and NIHSS at 90 days
- Correlation between infarct volume at 48 hours and BI at 90 days
- Correlation between infarct volume at 90 days and mRS at 90 days
- Correlation between infarct volume at 90 days and NIHSS at 90 days
- Correlation between infarct volume at 90 days and BI at 90 days

The sample SAS code is provided below:

3.4.4.3 Secondary Endpoints Analyses with Additional Covariates

The statistical models for one or more of the secondary endpoints may be amended to include additional covariates such as last known well time frame (≥ 6 hours or < 6 hours) and use of thrombolytics. This may be performed as post-hoc analyses.

3.4.5 Biomarker Endpoints

The protocol specifies that blood will be collected for Ribonucleic Acid (RNA) and other biomarker analyses. Statistical treatment of these biomarkers is outside the scope of analyses to be performed for inclusion in the Clinical Study Report. Nonetheless, some specification of biomarker analysis may be desirable, and this is provided in Appendix D.

3.5 Safety Assessment

Safety data will be summarized by actual treatment received and in total based on the Safety Population.

3.5.1 Adverse Events (AEs)

An AE is defined as any untoward medical occurrence in a subject or clinical investigation participant administered a pharmaceutical product and which does not necessarily have to have a causal relationship with this treatment.

An AE can therefore be any unfavorable and unintended sign (including an abnormal laboratory finding, for example), symptom or disease temporally associated with the use of a medicinal product, whether or not considered related to the medicinal product. AEs will be captured from the start of study drug infusion through study completion (Day 90). All AEs will be coded to system organ class and preferred term using MedDRA version 24.0. A medical review of the coding reports will be performed prior to database lock. Treatment-emergent adverse events (TEAEs) are defined as AEs that start after the study drug infusion.

The investigator will grade the intensity of the AE as mild, moderate, or severe.

The relationship of an AE to study drug will be assessed as related, possibly related, or unrelated.

An overview of AEs will be provided including counts and percentages of subjects (and event counts) with the following:

- Any TEAEs (overall and by maximum severity)
- Any study drug related TEAEs (overall and by maximum severity)
- Any SAEs
- Any treatment-emergent serious AEs (TESAEs)
- Any study drug related TESAEs
- Any TEAEs leading to discontinuation of study drug infusion
- Any AEs leading to death
- TEAE occurrence by Month (Day 0-Day 7, Day 8 – Day 14, Day 15 – Day 21, Day 22 – Day 30, Day 31-Day 60, and Day 61-Day 90)

Counts and percentages of subjects (and event counts) will also be presented by system organ class and preferred term for each of the categories in the overview. If more than one event occurs with the same preferred term for the same subject, the subject will be counted only once for that preferred term using the most severe occurrence for the summary by severity. The number of events will be presented for overall category of TEAE and for each system organ class and preferred term. The number of events will not be presented for each category of maximum severity. AE listings will include the following information:

- Subject ID
- Adverse event term
- Adverse event preferred term
- System Organ Class
- Start date
- Outcome
- End date
- Relationship to study drug
- Action taken with study drug

- Severity
- SAE Criteria

AEs with missing start dates will be considered as treatment-emergent. The first date of the month will be used to impute missing start days and January will be used to impute missing start months.

Listings will be presented specifically for SAEs and TEAEs leading to discontinuation of study drug.

3.5.2 *Clinical Laboratory Tests*

Blood for clinical laboratory tests will be collected at baseline and Day 2 and processed by the local laboratory. A list of laboratory tests to be performed and their standard units is included in Appendix A. Normal range files for local laboratories used in the study are provided by each site one time prior to database lock.

Absolute values and changes from baseline in standard unit will be summarized descriptively. The incidence of abnormalities (as defined by normal ranges) and clinical significances prior to the study drug infusion and after the study drug infusion will be summarized with counts and percentages of subjects.

3.5.3 *Vital Signs*

Blood pressure and heart rate will be measured at baseline, and per routine site standard of care, every 8-12 hours during Day 1 and Day 2 until completion of the infusion. Temperature will be recorded at baseline only if collected as standard of care. Since blood pressure and heart rate are measured every 8 hours during Day 1 and Day 2, the timepoints for the descriptive summarization of blood pressure and heart rate will be derived as follows:

Table 6: Vital Signs Timepoints derivation

| Derived Timepoint | Assessment Performed |
|-------------------|-----------------------------------|
| Hour 8 | After baseline and up to 12 hours |
| Hour 16 | 13 hours to 20 hours |
| Hour 24 | 21 hours to 32 hours |
| Hour 36 | 33 hours to 42 hours |
| Hour 48 | 43 hours and beyond |

Absolute values and change from baseline through the end of drug infusion of BP, heart rate, and temperature will be summarized using descriptive statistics by treatment group and time point. The number of available observations and out-of-range values (see Table 7) will be presented by treatment group and time point. Vital sign variables will be listed. Hypotension and hypertension thresholds are site dependent and evaluated by the investigator based on the individual's medical history and current status.

The maximum deviation of BP from baseline between study drug and placebo control group to Day 2 will be analyzed by an analysis of covariance (ANCOVA) model with treatment group as a factor and baseline BP as a covariate. The least-squares means, standard errors, and the 2-tailed 95% CIs for each treatment group and for each comparison will be presented. The two-sided p-values testing for significance within treatment group change from baseline and comparisons between treatment groups will be presented.

Table 7: Vital Sign range for out-of-range values determination:

| Variable | Range |
|--------------------------|--------------------------------|
| Systolic Blood Pressure | 90 to 140 mm Hg |
| Diastolic Blood Pressure | 50 to 90 mm Hg |
| Heart Rate | 60 to 100 beats per minute |
| Temperature | 96.8 to 100.4°F (36°C to 38°C) |

3.5.4 *Electrocardiograms (ECG)*

Electrocardiograms will be performed at baseline (within 4 hours of admission), 24h (\pm 4 hours), and 48h, \pm 4 hours).

Absolute ECG values will be listed. ECG parameters (heart rate, PR interval, QRS duration, QT interval, and QT interval corrected for heart rate using Fridericia's correction (QTcF) interval) values and overall interpretation will be summarized by treatment group and time point. QTcF is the duration of the QT interval corrected for heart rate by Fridericia's formula: $QTcF = QT/RR^{1/3}$

The number and percentage of subjects in each of the following categories will be presented by treatment and in total:

- Post-baseline absolute QTcF interval >450 msec
- Post-baseline absolute QTcF interval >480 msec,
- Post-baseline absolute QTcF interval >500 msec.
- Change from baseline QTcF interval increase >30 msec,
- Change from baseline QTcF interval increase >60 msec.

Clinically abnormal and significant results will be flagged.

3.5.5 *Physical Examinations*

Physical examinations will be performed at baseline and every 8-12 hours during Day 1 and Day 2. The investigator will grade the result of the physical examinations as normal, not clinically significant abnormal, or clinically significant abnormal. All clinically significant abnormal findings from the physical examinations will be flagged in data listings.

Since physical examinations are measured every 8-12 hours during Day 1 and Day 2, the timepoints for the summarization of physical examinations will be derived in the same manner as the vital signs timepoints provided in Table 6 of this SAP.

3.5.6 *Other Baseline and Safety Assessments*

Other baseline and safety assessments such as Non-contrast Computed Tomography Scan (NCCT) brain and Computed Tomography Angiography (CTA), hospitalization, CXR, EVT,

Telemetry, and Pregnancy testing results will be listed. Clinically abnormal and significant results will be flagged.

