8.2.1 Time Period and Frequency for Collecting AE and SAE Information

All SAEs will be collected from the start of study drug administration until Day 90, in addition SAE assessed as related to study drug or that have a fatal outcome will be collected to Day 90, see [Table 1-1: Schedule of Activities](#).

All AEs will be collected from the start of study drug administration through Day 90 at the time points specified in [Table 1-1: Schedule of Activities](#).

Medical occurrences that begin before the start of study intervention but after obtaining informed consent will be recorded in the Past Medical and Surgical History section of the electronic case report form (CRF), not in the AE section.

All SAEs will be recorded and reported to the sponsor or designee within 24 hours of knowledge of the event, as indicated in [Appendix 4: Adverse Events: Definitions and Procedures for Recording, Evaluating, Follow-up, and Reporting](#). The investigator will submit any updated SAE data to the sponsor within 24 hours of it being available.

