All participants, investigators, their clinical staff, local laboratories, study personnel, the data management group, and the sponsor staff and delegates will be blinded to the randomization codes and study drug assignment. All study personnel (Contract Research Organization (CRO) and Sponsor and sites) will remain blinded to this data until database lock, at minimum. In the event of emergency unblinding due to participant safety, the Investigator may request unblinding of that participant only. Processes and procedures for unblinding will be accordance with the study protocol, Data Management Plan, Safety Management Plan, and any applicable CRO or Sponsor Standard Operating Procedures.

2.2.3 *Study Drug*

RNS60 is [REDACTED]

[REDACTED] RNS60 has demonstrated exceptional safety in rodent and non-human primate toxicity studies. Additionally, RNS60 has demonstrated significant efficacy in a non-human primate model of acute ischemic stroke without any indications of adverse effects. In all clinical studies to date, RNS60 has been well tolerated. In this study, infusion will begin prior to the completion of the endovascular revascularization procedure (defined as the time of arterial access closure) and complete 48h after the infusion is initiated.

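### The SAP's treatment-emergent definition is ambiguous: read literally it leaves out dated events during the 48-hour infusion, and its partial-date rule can date in-trial AEs before dosing

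*SAP*

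**What the plan says.** SAP 3.5.1 opens the collection window at the start of dosing: "AEs will be captured from the start of study drug infusion through study completion (Day 90"). Protocol 8.2.1 agrees: "All AEs will be collected from the start of study drug administration through Day 90". It sends anything that begins between consent and dosing to the medical-history section of the case report form instead. So no AE record should have a true onset before infusion start.

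SAP 3.5.1 then defines the analysis subset: "Treatment-emergent adverse events (TEAEs) are defined as AEs that start after the study drug infusion". Neither the start nor the end of the infusion is named. SAP 2.2.3 has the infusion "complete 48h after the infusion is initiated".

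The overview that follows is built mostly on this subset: TEAEs, drug-related TEAEs, TESAEs, drug-related TESAEs, "Any TEAEs leading to discontinuation of study drug infusion", and TEAEs by time bin, with the first bin running from Day 0 to Day 7. Two rows are not restricted to TEAEs: any SAE, and AEs leading to death. The tables by system organ class and preferred term repeat the overview categories.

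For incomplete dates, SAP 3.5.1 first treats AEs with missing start dates as treatment-emergent. It then adds: "The first date of the month will be used to impute missing start days and January will be used to impute missing start months". No lower limit at the infusion date is given, and it is not stated whether a missing start date includes a partly missing one.

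**The concern.** Safety is the primary objective, and Protocol 2.3.1 names circulatory volume expansion or fluid overload as the major possible risk. The infusion is the period in which that risk would be expected to show. If a programmer takes the definition at its word, an event that starts at hour 20 of the infusion is an AE but not a TEAE.

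The overview has no row for all AEs and no discontinuation row outside the TEAE framework. A non-serious, non-fatal infusion-period event would therefore appear in no summary count. Yet the protocol synopsis lists discontinuations due to AEs as a safety outcome, and Protocol 9.3.3 includes AEs and discontinuations due to AEs in its primary analysis row. The SAP states that it overrides the protocol where they differ, so the protocol does not repair the definition.

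The partial-date rule is a smaller, separate problem. It can give an AE an onset date on which, by the collection rule, no AE could have been recorded.

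**Working it through.** The plan states no figure to reproduce here. The check applies the written rules and puts a size on each.

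**1. Two readings of the definition, against the same section.**

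| Item in SAP 3.5.1 | Anchor at end of infusion (literal) | Anchor at start of infusion |
|---|---|---|
| Capture from infusion start | First 48 h captured but not treatment-emergent | Consistent |
| TEAEs leading to discontinuation of infusion | Empty: an event that stops the infusion begins no later than the stop | Works |
| First TEAE bin, Day 0 to Day 7 | Opens with a stretch that can hold no dated TEAE | Works |
| Separate rows for any SAE and any TESAE | Rows differ | Rows coincide |

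The first three lines favour the start. The last is the one feature that could lead a programmer to treat TEAEs as a strict subset of AEs.

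**2. Length of the excluded period.** 48 / (90 × 24) = 2.2% of follow-up; 48 / (7 × 24) = 28.6% of the first week; and the whole of a planned exposure.

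**3. Patients at stake.** Inputs from SAP 2.2.4: 100 participants, and 20% anticipated to discontinue treatment for symptoms of fluid overload. Expected number: 0.20 × 100 = 20, with a 95% binomial range of 12 to 28. This assumes that each is recorded as an AE.
- Literal reading: 0 of about 20 count as TEAEs leading to discontinuation, so about 20 are lost.
- Start reading: all are eligible, so 0 are lost.

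**4. Partial dates.** Example: dosing on 15 October, AE recorded only as October. The imputed date is 1 October, 14 days before dosing. With 15 October as Day 1 and no Day 0 (SAP 3.1.1), that is Day −14, outside every bin. If the month is missing too, the date becomes 1 January.

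In general, an AE in the infusion month with its day missing is dated before dosing unless dosing was on the 1st, that is for 29 of 30 dosing days in a 30-day month.

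Across all onset months, assume that dosing dates are uniform over a 365-day year, onset is uniform within the window, and the remaining date parts are known. For onset k days after dosing, with k shorter than a month, the imputed date is not before dosing only if dosing was on the 1st (12 dates) or in the last k days of a month (12k dates):

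share before dosing ≈ 1 − 12(k + 1)/365.

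With day and month both missing, the same argument over the year gives 1 − (k + 1)/365. For onset on days 0 to 7 the average of k + 1 is 4.5, so the shares are 1 − 54/365 = 85.2% and 1 − 4.5/365 = 98.8%. Full enumeration of dosing dates gives:

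| Onset window after dosing | Day missing | Day and month missing |
|---|---|---|
| 0–2 days | 93.4% | 99.5% |
| 0–7 days | 85.2% | 98.8% |
| 0–30 days | 47.5% | 95.6% |
| 0–90 days | 16.2% | 87.4% |

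These shares are conditional on an AE having a partial start date. The documents give no frequency for that, so no number of patients follows.

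**The case against.** The strongest answer is that nobody would program the literal reading. Capture runs from infusion start, analysis days are counted from it (SAP 3.1.1), concomitant medication is anchored to it (SAP 3.3.5), Protocol 6.2 starts dose timing at infusion onset, and Protocol 8.1.2 treats findings after initiation of the infusion as post-dose. A planned row that would be empty is better evidence of a slip than of intent. This stands: a reader might infer that the SAP means to exclude infusion-period events, and the documents do not support that. What remains is that the one sentence fixing the flag omits the anchor, although the SAP names it elsewhere, including the end of infusion where the end is meant (vital signs, Table 1 footnote 6).

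A reader might also infer that about 20 patients would vanish from the primary safety analysis. They would not. The proportion with SAEs to Day 90 and 90-day mortality (SAP 2.3.1, 3.4.1) do not use the TEAE flag, nor do the any-SAE and AEs-leading-to-death rows. The general AE listings are not limited to TEAEs and show action taken with study drug. Only the dedicated listing of discontinuations is TEAE-based.

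On partial dates, the sentence before the imputation rule may already protect the flag. Site queries before lock (SAP 3.1.6) and the use of hospital records for in-hospital AEs (Protocol 8.2.2) should make partial dates uncommon, perhaps most of all for early events. This also stands, and it limits the number affected. It does not give the imputed date a floor.

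**Conclusion.** The definition is wrong as written and inconsistent with the tables it feeds, though most likely by omission. The effect on anticipated fluid-overload discontinuations in the TEAE and discontinuation tables is 0 under the start reading and about 20 of 100 under the literal one. The upper figure rests on the plan's own 20% and on each case being recorded as an AE. AEs with fully missing start dates are an exception, since they count as treatment-emergent by rule.

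The partial-date defect holds under either reading. An AE in the infusion month with its day missing is usually dated before dosing and falls outside every TEAE time bin. If the missing-date sentence covers only fully missing dates, such an AE also loses its TEAE flag. The percentages should not be read as the share of all AEs misdated: they apply only to AEs with partial dates, and with only the day missing they fall to 16.2% when onset is spread over 90 days.

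The point should be corrected because safety tabulation is the purpose of the trial. It is not a threat to the primary endpoints.

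**What to change.** Make two changes in SAP 3.5.1.

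1. Define a TEAE as an AE with onset at or after the start of study drug infusion. The words at or after matter if onset is compared by date only, because a strict comparison would drop events on the day of dosing.
2. Impute a partial AE start date as the later of the first day of the known month (or of the known year) and the infusion start date, whenever the known parts are compatible with onset on or after infusion start. State that the treatment-emergent rule covers partly as well as fully missing dates.

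Two consequences to note. With a start anchor, the SAE and TESAE rows coincide, so one can go. Floored dates will collect in the first time bin, so a footnote should give the number of imputed dates. While the text is open, the first bin should also be aligned with SAP 3.1.1, which has no Day 0.

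The cost is two sentences and about one line of programming, with no change to design or data collection. It can be made as a SAP revision or addendum.
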